3. TRIAL FLOW CHART

4. TRIAL SUMMARY

Title	The influence of anaesthetic depth on patient outcome after major surgery (The BALANCED anaesthesia study)
Project Office	Department of Anaesthesia and Peri-operative Medicine, Auckland City Hospital, [name]. [contact] [name], [contact], [contact]
Study Size	6,500 patients
Study Design	International multicentre double blind, prospective, intention to treat, safety and efficacy study
Primary Outcome	One year all-cause mortality
Secondary Outcomes	MI, cardiac arrest, pulmonary embolism, stroke, sepsis, surgical site infection, ICU stay, hospital stay, awareness, WHODAS score, persistent postoperative pain and cancer recurrence
Inclusion Criteria	≥60 years, ASA physical status 3 or 4, surgery lasting ≥2 hours, post-op hospital stay ≥2 nights, general anaesthesia with or without major regional block, able to monitor BIS
Study Protocol	
Pre-operative	Age, sex, weight, height, ASA physical status, ECG, haemoglobin, creatinine, albumin, Charlson co-morbidity score, WHODAS 12 item score
Intra-operative	Pre-defined mean arterial blood pressure target Randomised BIS target of 35 or 50 Computerised recording of BIS, SR, BP, HR, ETvol conc. Manual record of drugs administered and recovery indicators
Post-operative day 1-3	QoR-15 score, Analgesic and antiemetic requirements MI, cardiac arrest, pulmonary embolism, stroke, sepsis, surgical site infection, awareness (once)
Hospital Discharge	Length of hospital stay, unanticipated ICU admission, ICU stay, unplanned second operation
Post-operative day 30	Survival and disability free survival MI, cardiac arrest, pulmonary embolism, stroke, sepsis, surgical site infection, awareness, QoR-15 score, WHODAS 12 item score, persistent postoperative pain, staging of cancer
1 year follow-up	Survival and disability free survival MI, cardiac arrest, pulmonary embolism, stroke, sepsis, surgical site infection, WHODAS 12 item score, persistent postoperative pain, cancer recurrence

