8. AIM OF TRIAL

Recent observational studies have found an association between deep anaesthesia and increased post-operative mortality in elderly and infirm patients undergoing major surgery. It is unknown whether there is a causal relationship in this observation, which occurs at levels of anaesthetic depth that are within the normal range of practice. We are performing a large randomised trial of 'deep' versus 'light' anaesthesia to definitively answer the question of whether anaesthetic depth alters perioperative outcome. Elderly patients undergoing major surgery will be randomised to an anaesthetic targeting either BIS=35 or BIS=50 for the deep and light groups respectively. The primary outcome variable will be all-cause mortality at one year and secondary outcomes will be MI, cardiac arrest, PE, stroke, sepsis, surgical site infection, ICU stay, hospital stay, awareness, WHODAS score, persistent postoperative pain and cancer recurrence.

Primary hypothesis

Light general anaesthesia (BIS = 50) is associated with decreased all cause mortality compared with deep general anaesthesia (BIS = 35) one year after major surgery in elderly patients.

Secondary hypotheses

Light general anaesthesia (BIS = 50) is associated with decreased incidences of MI, cardiac arrest, PE, stroke, sepsis and surgical site infection compared with deep general anaesthesia (BIS = 35) at 30 days and one year after major surgery in elderly patients.

Light general anaesthesia (BIS = 50) is associated with decreased incidences of a composite endpoint of MI, cardiac arrest, PE and stroke compared with deep general anaesthesia (BIS = 35) at 30 days and one year after major surgery in elderly patients.

Light general anaesthesia (BIS = 50) is associated with decreased cancer recurrence compared with deep general anaesthesia (BIS = 35) one year after major surgery in elderly patients.

Light general anaesthesia (BIS=50) is associated with an increased incidence of persistent postoperative pain compared with deep anaesthesia (BIS=35) at 30 days and one year after surgery in elderly patients.

Light anaesthesia (BIS = 50) is associated with increased disability-free survival compared with deep general anaesthesia (BIS = 35) one year after major surgery in elderly patients.

Safety and quality hypotheses

Light general anaesthesia (BIS = 50) is associated with improved early quality of recovery compared with deep general anaesthesia (BIS = 35) after major surgery in elderly patients.

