- 10. WHODAS score: pre-operative, day 30 and 1 year
- 11. **Disability free survival**: disability-free survival up to 1 year: survival and freedom from new-onset disability, the latter defined as a 4-point reduction in the WHODAS score [56]. Disability in the WHODAS score is self reported by the participant, if the participant is unable to complete the score, then we will use a proxy's report as per WHODAS standard procedures. The date of onset of new disability will be recorded.
- 12. **Persistent post-operative pain**: pain over the surgical site, for at least three months after surgery, that cannot be explained by other causes, such as disease recurrence or a pre-existing pain syndrome.
- 13. **Cancer recurrence:** defined as clinical radiological or pathological evidence for recurrence of the tumour either at the local or a distant site.

Inclusion criteria

Age ≥ 60 years, ASA physical status 3 or 4, surgery expected to last ≥ 2 hours, post-operative hospital stay expected to be ≥ 2 nights, general anaesthesia with or without major regional block, able to monitor BIS throughout anaesthesia.

Exclusion criteria

Unable to monitor BIS (e.g. cranial or intracranial surgery), unable to consent, surgery with 'wake-up' test, propofol infusion for part or all of maintenance of anaesthesia ('total intravenous anaesthesia'), previous enrolment in Balanced study.

Intervention

General anaesthesia monitored with BIS. BIS targets will be either 50 or 35. We expect 90% of anaesthesia time to be within 5 units of the target BIS value and no deviations for >5 minutes.

Consent

Patients who are eligible for the trial will be given the patient information sheet by a member of the research team and encouraged to discuss the study with their family (or family/whanau in New Zealand) before written informed consent is sought, in accordance with local practice.

Treatment allocation

Once all entry details are recorded and eligibility confirmed, randomisation will be performed by contacting the automated on-line randomisation service with back-up phone service. Assignment to one of the two groups will be stratified by collaborating centre and a unique study number assigned. Investigators and research staff involved in patient followup are blinded to treatment allocation.

Perioperative Care

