Post-operative day of discharge Length of hospital stay, unanticipated ICU admission, ICU stay, unplanned second operation

Post-operative day 30

Survival, ongoing analgesic or antiemetic requirements. Incidence of MI, cardiac arrest, PE, stroke, sepsis, surgical site infection, awareness, QoR-15, WHODAS score, persistent post-operative pain and other adverse events, staging of cancer (in cancer patients).

Post-operative one year

Survival. Disability free survival.

Incidence of MI, cardiac arrest, PE, stroke, sepsis, surgical site infection, WHODAS score, persistent post-operative pain (using modified pain inventory and neuropathic pain questionnaire if there is pain present [59,60])

In cancer patients, definitive Tumour-Node-Metastasis staging of cancer and evidence of any recurrence

All these measures are in frequent use and have been validated in past studies both of anaesthetic outcome as already discussed and in the general medical literature. Definitions of outcomes will be those used in the current ENIGMA-II Trial (a study of the influence of nitrous oxide on long term outcome from anaesthesia) and RELIEF trial [61] (see appendix).

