13. SAMPLE SIZE AND STATISTICAL ANALYSIS

Primary outcome

One year all-cause mortality will be compared between randomised groups using a Mantel-Haenszel Chi-square test, stratified by study centre. A two-tailed p-value <0.049 will be taken to indicate statistical significance.

Power analysis

One year all-cause mortality is expected to be ~10% based on the findings of Leslie et al's study and Australasian studies [9,25]. The reduction in mortality in the light anaesthesia group is expected to be 20%. A power analysis using p1=0.10 and p2=0.08 indicates that N=3250 patients are required in each group, β =0.8, α =0.049. The alpha level is reduced to allow for the single interim analysis.

The primary and secondary outcomes will initially be analysed using the full analysis set population i.e. using those individuals who have confirmed outcomes. Sensitivity analyses will also be undertaken, as appropriate, for which those missing outcome data will be assigned a poor outcome. Complete listings, according to randomised group, will be compiled of those lost to follow-up, and include relevant explanations.

Secondary outcomes

The presence of MI, cardiac arrest, stroke, PE, sepsis, surgical site infection, awareness and persistent post-operative pain at 30 days and one year as appropriate will be compared between randomised groups using Mantel-Haenszel chi-square tests or Fisher's exact test depending on the expected cell frequencies. Additionally a composite score including the presence of any of MI, cardiac arrest, stroke and PE, will be compared between randomised groups also using a chi-square test.

Additional analyses will also explore the role of MI, cardiac arrest, stroke, PE, sepsis, surgical site infection and cancer recurrence on one year mortality using Cox's proportional hazards regression to develop a model of independent predictors of one year mortality. The randomised group will be added to this model to assist explanation of any observed differences in outcome between the randomised groups.

Secondary analyses will be undertaken on an intention to treat basis. The vast majority of participants will have assessments of the primary outcome (one-year mortality) and the 30-day secondary outcomes. Permission will be sought as necessary to extract these from national databases and local hospital records.

Adverse events

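### Persistent post-operative pain is defined by at least three months of pain, yet the protocol hypothesises and records it at day 30, when no patient can meet the definition

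*Protocol*

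**What the plan says.** Section 10, secondary endpoint 12, sets the definition: "pain over the surgical site, for at least three months after surgery, that cannot be explained by other causes". It gives no separate definition for an earlier time point.

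Three other places attach the same outcome to day 30:

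- Section 8, secondary hypotheses, predicts for light anaesthesia an "increased incidence of persistent postoperative pain compared with deep anaesthesia (BIS=35) at 30 days and one year after surgery".
- Section 4, trial summary, day-30 row, lists "awareness, QoR-15 score, WHODAS 12 item score, persistent postoperative pain, staging of cancer".
- Section 10, Recordings, post-operative day 30, lists "awareness, QoR-15, WHODAS score, persistent post-operative pain and other adverse events".

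Section 13 then names the outcomes to be tested between groups, ending with "awareness and persistent post-operative pain at 30 days and one year as appropriate will be compared".

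The study flow chart in the appendices schedules the modified brief pain inventory (mBPI), if needed, at day 30 and at one year. It schedules the neuropathic pain questionnaire, if needed, at one year only. It shows no visit between day 30 and one year.

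**The concern.** The endpoint has a minimum duration that is longer than the follow-up at the first of its two stated time points. The definition and the 30-day hypothesis cannot both be followed.

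It matters because this is the only hypothesis in section 8 that predicts more of an adverse outcome under light anaesthesia, so it bears on how benefit and harm are weighed. The background in section 9 says that light anaesthesia may increase post-operative pain, and it reviews small studies of early pain and analgesic use with mixed results. A 30-day difference is therefore a reasonable question, but a different one from persistent pain. If pain present at day 30 is counted under the persistent-pain label, an early difference could be reported as a lasting one. If the definition is applied strictly, the 30-day table is empty, and an empty table is not evidence of no harm.

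**Working it through.** The protocol states no expected incidence or power for persistent pain, so there is no figure of its own to reproduce. Its only power calculation (3,250 per group, 10% against 8% one-year mortality) takes no input from pain.

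**Step 1: timing.** Inputs are the minimum duration of three months (section 10, endpoint 12) and the assessment at day 30 (sections 4, 8 and 10).

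- Three months as 3 × 30 = 90 days. Shortfall: 90 − 30 = 60 days.
- Three months as 3 × 365/12 = 91.25 days. Shortfall: 91.25 − 30 = 61.25 days.
- The shortest conceivable reading, 3 × 28 = 84 days, still leaves 84 − 30 = 54 days.

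No reading of three months lets a patient qualify at day 30.

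**Step 2: the test under the written definition.** The event count is 0 in each arm and in every centre. For centre *i* with total N, arm sizes n₁ and n₀, and total events m₁ = 0:

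- Mantel-Haenszel numerator: Σ(a − n₁m₁/N) = Σ(0 − 0) = 0.
- Mantel-Haenszel variance: Σ n₁n₀m₁(N − m₁)/[N²(N − 1)] = 0.
- The statistic is 0/0, which is undefined. Fisher's exact test on the same table returns p = 1.

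Any non-zero count at day 30 must therefore come from another endpoint.

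**Step 3: what the day-30 instrument measures.** The mBPI items in appendix 23.5 ask about pain in the last 24 hours or at the moment. At day 30 they capture current pain, for which the protocol has no endpoint definition.

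**Step 4: what section 13 commits to.** Its sentence gives one pair of time points for eight outcomes, with a qualifier. Awareness is among the eight. The flow chart schedules the awareness questionnaire on day 1 and day 30 only, and the one-year list in section 10 omits it. So the qualifier must assign time points outcome by outcome. For pain there are two readings:

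| Reading of section 13 | Consequence |
|---|---|
| Pain tested at 30 days and one year | The 30-day test is empty or uses an undefined endpoint |
| Pain tested at one year only | The 30-day part of the section 8 hypothesis has no test |

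The contradiction survives under both.

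**Step 5: the one-year comparison.** One year exceeds three months, so the definition can be met then. The day-30 wording does not alter that comparison.

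**The case against.** The strongest reply is that section 13 already deals with this. Because its qualifier has to drop awareness at one year, it can equally drop persistent pain at 30 days, and a sensible analyst would read it so. That is fair, and it stands as far as section 13 goes: the protocol does not firmly commit to a 30-day test. It does not reach section 8, which names 30 days for this outcome specifically, or the two day-30 lists.

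A second reply is that nobody would apply a three-month criterion literally at day 30, and that a result labelled as a 30-day result would not be mistaken for chronic pain. This reduces the likely harm. It also concedes that the day-30 measure is a different endpoint, which the protocol leaves undefined.

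A third is that a statistical analysis plan, not available for this review, may settle the matter. It could, but only by overriding either the definition or the hypothesis as written.

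Several stronger readings are tempting and are not supported:

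- A reader might infer that the pain results as a whole are compromised. The one-year comparison can still meet the definition, and the mBPI is already scheduled at both visits.
- A reader might infer that the 30-day measure is acute pain or reflects short-term analgesia. The protocol says neither. Pain at 30 days that does not meet the definition is as far as the text goes.
- A reader might infer that the harm assessment of light anaesthesia rests on this outcome. Awareness is a separate safety hypothesis in section 8.

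**Conclusion.** The contradiction is real and rests on the protocol's own wording alone. Under the written definition the attainable 30-day count is 0 in each arm, so one of the two time points in the section 8 pain hypothesis cannot be examined as defined. That zero is a matter of logic and is not an estimate of bias or lost power.

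The reach is limited. Persistent pain is one of 13 secondary endpoints and has no power calculation or alpha allocation of its own. The primary outcome, its sample size and its significance level are not affected, nor is the one-year pain comparison. This is a moderate secondary-endpoint error that should be corrected before analysis. It would be too strong to call it a must-fix design fault.

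The conclusion assumes that endpoint 12 is the only definition of persistent pain in force; none other appears in the protocol.

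**What to change.** 1. Restrict persistent post-operative pain to the one-year assessment in section 4 (day-30 row), section 8 (pain hypothesis), section 10 (endpoint 12 and the day-30 recordings) and section 13.
2. Analyse the day-30 mBPI data as a separately named secondary outcome, *surgical-site pain at 30 days*, with its own short definition. That definition should say how pain is attributed to the surgical site, since the mBPI items as shown do not ask this. If a 30-day hypothesis is wanted, state it for this outcome.
3. Optionally, add one case report form item at one year confirming that the pain has lasted at least three months. The mBPI looks back 24 hours at most, and the neuropathic questionnaire as shown asks whether the pain was there before surgery but not how long it has lasted.

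Item 1 is wording only. Item 2 is wording and one extra table, with no new visit because the instrument is already scheduled at day 30. Item 3 is a small added cost: a new question at an existing visit.

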11. EXPERIMENTAL CONTROL

Ethics committee approval for the pilot study was obtained from the Northern X Regional Ethics Committee in New Zealand and also ethics committees in Victoria, Western Australia and Hong Kong.

This trial will require approval from each site's ethics committee. Written informed consent will be required from all participants. The Data Monitoring Committee will review the safety of the trial as well as the interim analysis as soon as it becomes available.

12. BIAS CONTROL

a) *Bias Control.* The study is a comparison of two levels of depth of anaesthesia. The alternative of comparing deep and light groups with standard of care was considered. Knowing that the trial is a comparison with a BIS targeted group would also introduce a source of bias to the study. We would still need to collect BIS and volatile usage data to know at what depth the control anaesthetics were maintained, to detect this. The option of concealing the BIS data from the anaesthetist would be difficult to achieve in the large pragmatic study as proposed and would introduce another source of bias, namely that the anaesthetist may be deprived of this information which they may have otherwise used.

b) *Blood pressure management.* There is a potential confounding effect of blood pressure. Low blood pressure during anaesthesia is also associated with poor outcomes and more likely to occur in the "deep" anaesthesia group. We do not have audit data available on "usual" blood pressures during anaesthesia, for example, but the lack of standardisation of blood pressure in an open control group would further increase the variability in the sample, and therefore the numbers needed to detect a difference, if one exists.

c) Volatile anaesthetic use. Past observational studies have found an association with low BIS and low volatile anaesthetic requirement (low MAC). This may be a spurious association, and our trial design is capable of detecting these individuals and determining whether this observation is causal.

d) *Is this standard practice?* There is a possibility that neither group may be relevant as standard practice; this fear is probably unfounded. Currently, there is no standard for optimum anaesthetic depth, and so it is not surprising that a wide large range of depths, below the level associated with awareness, are employed by anaesthetists. Because no other variables or anaesthetic techniques are prescribed in the trial, the anaesthetics given should be relevant. We confirm that we are asking for blood pressure targets to be prescribed, but not stating what they should be, to allow clinicians to make their own judgement as to the optimum blood pressure for each patient. Consequently, this will prevent blood pressure differences between the groups becoming a source of bias.

e) Accurately tracking the two BIS targets Accurately tracking BIS at either 35 or 50 requires more attention to detail with drug dosage than is usual during general anaesthesia. We plan to monitor BIS tracking at all sites using de-identified BIS traces. We expect the average BIS value during the maintenance phase of anaesthesia to be within 5 units of target for 95% of patients. During the maintenance phase of the anaesthetic, we expect deviations more than 10 units from target to persist for no longer than 5 minutes 95% of the time. Sites unable to maintain this degree of accuracy may be closed down.

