been published using available databases. Five of these have found similar increases in mortality. In Lindholm et al.'s study, deep hypnotic time was not a predictor when pre-existing malignancy was included in the model. If deep hypnotic time was >2 hours subsequent mortality was much higher. Searleman et al.'s study found that non-surviving patients received slightly less volatile anaesthetic than the survivors, implying that patients who died may have been sensitive to the anaesthetic drugs. Saager et al.'s study used a very large database with 24,000 patients, and found three independent predictors of increased one year mortality, which were minimum alveolar concentration (MAC) <0.4, mean arterial pressure (MAP) <80 mmHg and BIS<40. (MAC is a normalised measure of anaesthetic potency). The risk to those who received deep anaesthesia was again a 20% increase in one-year mortality. Patients with a low MAP during the procedure faired even worse, and the combination of all three factors was associated with a RR=1.6 for one year mortality. They also found that patients who had an instance of low MAP, which was treated within 5 minutes had improved outcomes, indicating that although patients who were sensitive to anesthesia did poorly, early intervention was effective. Leslie et al analysed long-term outcomes in the B-Aware Trial, a 2,500 patient trial conducted principally in New Zealand, Australia and Hong Kong. This study also found an increased risk of myocardial infarction and cerebrovascular accident in the deep anaesthesia group. There were a large number of cardiac patients in the study and the same relationship of depth with poor outcome was confirmed, a finding repeated by Kertai et al. [17].

Author	Ν	ASA	1 y	Increased risk of
		3&4 *	mortality	death if 'deep' [#]
Monk 2005 [12]	1064	35%	5.5	RR = 1.24
Lindholm 2009 [13]	4087	6%	4.3	HR = 1.18
Saager 2009 [14]	23,999	~30%	4.8	RR = 1.63
Searleman 2010 [15]	1791	71%	10.7	OR = 1.25/h
Leslie 2010 [16]	2463	74%	10.8	PS = 1.42 (at 4y)
Kertai 2010 (cardiac) [17]	460	100%	17.8	HR = 1.29 (at 3y)
Kertai 2011 (non-cardiac) [18]	1473	60%	24.3	HR = 1.03 (at 3y)

TABLE 1 Observational studies of the relationship between depth of anaesthesia and subsequent mortality

*ASA=American Society of Anaesthesiologists physical status scale, 1=normal health, 2=mild to moderate systemic disturbance, 3=severe systemic disturbance which limits activity, 4=incapacitating life threatening disease, 5=moribund.

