Figure 2

30-day mortality in patients who had a mean MAC=0.6 during their anaesthetic (the low group). The figure demonstrates the marked effect of either low BIS or low MAP and mortality [40].

A much larger study of postoperative delirium and cognitive decline in 921 patients aged over 60 years and undergoing major non-cardiac surgery has compared BIS guidance between 40 and 60 with standard of care and BIS concealment [44]. Patients in the control group had lower BIS values (mean 36) compared to the treatment group (mean 53). There was a 30% reduction in volatile anaesthetic use, significantly less delirium in the BIS guided group (16% vs 24% incidence) and significantly less postoperative cognitive dysfunction at three months (10% vs 15% incidence). Most patients were ASA physical status 1 and 2. The study was not powered to detect a difference in mortality, but interestingly found evidence of predominantly deep anaesthesia in the control group, when anaesthesia was not BIS guided.

A pilot study of the proposed trial methodology

A pilot study of 125 patients has been completed at six hospitals in New Zealand, Australia and Hong Kong [45]. The study was approved as meeting current ethical committee requirements in all three jurisdictions, and was also approved by the Māori research review committee at Auckland District Health Board. The study protocol was found to be acceptable to our patients and anaesthetists and no ethical concerns were raised. The results reassured us that BIS targets could be met, that a lower blood pressure in the 'deep' group was not a confounding factor and demonstrated a 50% higher anaesthetic dose in the deep group (Table 3). The pilot study also allowed us to refine details of the protocol and perform an accurate costing.

A summary of one-month and one year outcomes is presented in Table 4. It must be noted that although there are differences in the two groups in one of these outcomes, the study is under powered to attach any significance to this difference.

	BIS 35	BIS 50
Ν	61	64
Duration (min), mean (sd)	198 (79)	196 (105)
BIS (mean (sd) of means)	39 (5)	48 (6)
MAC (mean (sd) of means) *	0.95 (.23)	0.63 (.19)
MAP (mean (sd) of means) [#]	86 (11)	89 (10)

TABLE 3: Pilot study, depth, volatile anaesthetic dosing and mean arterial pressures

*MAC is minimum alveolar concentration of anaesthetic vapour. *MAP is mean arterial pressure

TABLE 4: One month and one year outcomes in the pilot study

Outcome		BIS 35	BIS 50

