Anaesthesia will consist of standard anaesthetic hypnotics, volatiles, opioids and relaxants, intravenous or inhalational induction, volatile maintenance, opioids and muscle relaxants, with continuous BIS monitoring. No use of nitrous oxide will be allowed due to its interference with accurate BIS readings and similarly no infusions of ketamine above 25 mg/h will be allowed.

An individualised mean arterial blood pressure target range appropriate for the patient being studied will be set by the anaesthetist before BIS target randomisation. Anaesthetists will be encouraged to maintain patient normothermia and to give DVT prophylaxis and antibiotic prophylaxis as per local institutional practice. Other aspects of anaesthesia and perioperative care will be at the discretion of the anaesthetist. All complications (including those defined as secondary outcomes) will be managed according to routine institutional practice.

Recordings

Data will be collected by interviewing patients, relatives and doctors, and by review of hospital medical records and national databases (if applicable). Source documentation may be requested for any or all data recorded. Any or all data recorded may be subject to assessment by the Endpoint Adjudication Committee (on the direction of the Steering Committee).

Pre-operative

Age, sex, height, weight, ASA physical status, electrocardiogram (ECG), haemoglobin, creatinine, albumin, updated Charlson co-morbidity score [57,63], WHODAS-12 score

Intra-operative

Electronic *or* printed record with minimum of 5 minutely recording of BIS, burst suppression ratio (SR), end-tidal volatile anaesthetic concentration, mean arterial blood pressure and heart rate.

Manual record of all drugs used, including total dose of opioids used and regional or local anaesthetic blocks used.

Recovery

Analgesic and antiemetic requirements, time of arrival and eligibility for discharge.

Post-operative days 1, 2, 3

Routine laboratory testing.

Incidence of MI, cardiac arrest, PE, stroke, sepsis, surgical site infection and other adverse events.

Questioning for evidence of awareness under anaesthesia using the modified Brice questionnaire administered once, preferably on the day following surgery.

Analgesic and antiemetic requirements.

Quality of recovery: A validated post-operative quality of recovery score, the QoR-15 score will be recorded [58].

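### Section 12c claims a causal answer about low volatile requirement, but randomising the BIS target supports one about depth only

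*Protocol*

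**What the plan says.** Section 12 (Bias Control), item c, is headed as concerning volatile anaesthetic use. It opens: "Past observational studies have found an association with low BIS and low volatile anaesthetic requirement (low MAC"). It allows that the association may be spurious, and then says that "our trial design is capable of detecting these individuals and determining whether this observation is causal".

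Other parts of the protocol bear on this claim:

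- Section 10, Intervention: "BIS targets will be either 50 or 35". Under Treatment allocation: "Assignment to one of the two groups will be stratified by collaborating centre". Nothing else is randomised or stratified.
- Section 12e: "Accurately tracking BIS at either 35 or 50 requires more attention to detail with drug dosage than is usual during general anaesthesia". Drug dose is thus the means of reaching the allocated target.
- Section 10, Recordings: end-tidal volatile concentration is an intra-operative measurement. The study flow chart in the appendices puts randomisation in the pre-operative column.
- Section 10, Perioperative Care: opioids are part of the anaesthetic, and "Other aspects of anaesthesia and perioperative care will be at the discretion of the anaesthetist".
- Section 9, pilot study: the results "demonstrated a 50% higher anaesthetic dose in the deep group" (Table 3).
- Section 9, observational studies: one of the predictors of one-year mortality in a large database study was "minimum alveolar concentration (MAC) <0.4".
- Section 15: randomising to two doses, in place of two depths, was considered and not adopted.

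**The concern.** Low volatile requirement is a characteristic of the patient. The trial sees it only through the dose the patient was given, and that dose depends on the allocated target, on the patient's sensitivity, and on other drugs left to the anaesthetist. A given low MAC at BIS 35 marks a more sensitive patient than the same MAC at BIS 50.

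Two comparisons might seem to deliver what 12c promises. Comparing low-MAC with other patients inside one arm repeats the observational association. Comparing low-MAC patients between arms conditions on a variable that the allocation has moved, so it sets different kinds of patient against each other. Randomisation protects neither.

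Low MAC together with low BIS is among the observations that motivate the trial (section 9, text on the observational studies and Table 2). Section 9 itself suggests that the link with death reflects intolerance of anaesthesia, possibly as a marker of illness. If that is right, a low-MAC subgroup could show higher mortality in the deep arm even when depth does nothing, and 12c as worded would lend that result a causal reading.

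**Working it through.** **1. The protocol's own figures.** From Table 3, 0.95 / 0.63 = 1.51, which agrees with the stated 50% higher dose. The sample size in section 13 also reproduces: for 10% v 8%, two-sided alpha 0.049 and 80% power, the usual formula gives 3,233 per arm against the stated 3,250, and power at 3,250 is 80.2%. The randomised depth comparison is sound on its own inputs.

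**2. Does allocation move MAC?** Difference = 0.95 − 0.63 = 0.32. Standard error = √(0.23²/61 + 0.19²/64) = 0.038. The 95% interval is about 0.25 to 0.39 (z about 8.5). It clearly does.

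**3. Who falls below a common MAC cut?** Treat each arm's patient means as normal with the pilot mean and SD. The share below cut t is Φ((t − 0.95)/0.23) at BIS 35 and Φ((t − 0.63)/0.19) at BIS 50. Multiply by 3,250 for counts.

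| MAC cut | BIS 35 | BIS 50 | Counts | Ratio |
|---|---|---|---|---|
| 0.4 | 0.8% | 11.3% | 27 v 367 | 13.5 |
| 0.5 | 2.5% | 24.7% | 82 v 802 | 9.8 |
| 0.6 | 6.4% | 43.7% | 208 v 1,421 | 6.8 |

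At 0.4 the cut lies (0.4 − 0.95)/0.23 = −2.4 SD from the deep-arm mean, but only (0.4 − 0.63)/0.19 = −1.2 SD from the light-arm mean. The same cut selects a more extreme group in the deep arm.

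The deep-arm count at 0.4 is a far-tail estimate from 61 patients. The 95% interval for that SD alone, about 0.195 to 0.28, moves the count from about 8 to about 80.

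**4. Could this produce a false signal?** Take a null case. Depth has no effect on death, overall mortality is 9%, and one standard normal sensitivity score S fixes MAC as 0.95 − 0.23·S in the deep arm and 0.63 − 0.19·S in the light arm. S raises the odds of death by an assumed ratio per SD. Simulated mortality among patients with MAC <0.4:

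| Odds ratio per SD | Deep | Light | Deep/light |
|---|---|---|---|
| 1.0 | 9.0% | 9.0% | 1.00 |
| 1.25 | 15.1% | 12.4% | 1.22 |
| 1.5 | 21.9% | 15.7% | 1.40 |
| 2.0 | 35.2% | 21.4% | 1.65 |

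Every ratio above 1 is artefact, and all point in the direction of the primary hypothesis. At cuts of 0.5 and 0.6 the ratios are similar or slightly larger (1.23, 1.43 and 1.75 at 0.6). The odds ratios are assumptions, since the protocol gives none.

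**The case against.** The strongest reply is that 12c is loosely worded and can be read more kindly. It names low BIS as well as low MAC, calls the association possibly spurious, and sits in a section on bias. Section 9 asks whether avoiding relative overdose or low BIS values would make a difference. Randomising the BIS target answers that, because sensitive patients are balanced between arms in expectation. This stands for depth. It does not rescue the sentence as it refers to volatile requirement: the item is headed for volatile use, names low MAC, and speaks of detecting the individuals concerned.

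A reader might also infer that the trial report would draw a causal conclusion from a low-MAC subgroup. The protocol does not support that. Section 13 compares randomised groups, and its exploratory Cox model lists clinical events and randomised group, with no MAC term. The nearest item is a possible secondary study in section 16, and section 21 requires a separate, approved protocol for investigators' secondary analyses. The absence of a planned MAC analysis is no fault either, since a statistical analysis plan may cover it.

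Nor should 27 against 367, or a 13-fold difference, be read as a forecast. The 0.4 cut comes from a cited study and the trial never adopts it. The caption to Figure 2 describes a mean MAC of 0.6 as the low group.

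Finally, it would go too far to say that sensitive patients cannot be compared across arms at all. Ranking MAC within arm, or a principal-stratum analysis, could explore whether the depth effect differs in them. Such work needs untestable assumptions, such as rank preservation, and would still not show that low requirement causes death.

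**Conclusion.** The concern holds as an overclaim in one sentence of 12c. The design supports a causal conclusion about the randomised depth target. It gives no randomised comparison for volatile requirement, because MAC is measured after randomisation and shifts with the arm by about 0.32.

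The shift itself rests on the pilot data. The subgroup percentages rest also on normality and on cuts that the trial has not adopted. Their size is uncertain, but the direction is the same at 0.4, 0.5 and 0.6. The spurious mortality ratios of 1.22 to 1.65 depend on assumed links between sensitivity and death and vanish if there is none. The primary analysis and sample size are untouched. The correction matters for how any later analysis by volatile use is interpreted.

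**What to change.** Replace the closing claim of 12c with wording such as: the trial tests whether the randomised BIS target affects mortality; volatile requirement is observed after randomisation and depends on the allocated target, so any analysis by volatile requirement is exploratory and non-causal.

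Add that such an analysis should define low requirement relative to the patient's own arm, and not by one absolute MAC cut. The lowest fifth of mean MAC within each arm is one option; the choice can be left to the analysis plan or a substudy protocol. Associations with outcome would be reported within each arm, with no causal claim between arms.

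The cost is a wording change. The data are already collected, and what is given up is a claim that the design cannot support.
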